Also addressing to the new national healthcare system number 27, 2014 regarding Technical Instructions System of Indonesian Case Base Groups, where medical coverage is not based on medical expenses but the grouping of diagnoses and treatment based on ICD-9, the high cost of medical products often complicate the hospital policy.¹¹

Therefore, as suggested by the Indonesian Ministry of Health, we are going to use our local plate and screw for maxillofacial fractures management to answer the balance of supply and demand of local medical products. On the other hand, it could help the government to reduce medical expenses.

Aim Of The Study

The aim of this experiment is to investigate the usage of the locally-made miniplate and screw are not inferior compared to the existing benchmark miniplate and screw in terms of bone healing, surrounding tissue reactions, and screw loosening.

Study Hypothesis

The locally-made miniplate and screw are not-inferior compared to the existing benchmark miniplate and screw in terms of bone healing, surrounding tissue reactions, and screw loosening.

OBJECTIVES AND OUTCOMES

Primary Objective

To evaluate bone density radiologically (in Houndsfield Unit) after plate and screw fixation with locally-made compared to existing benchmark miniplate and screw

Secondary Objective

- To evaluate if there is any loosening screw following both locally-made and existing benchmark miniplate and screw fixation.
- To evaluate if there is any sign of local tissue reaction following both locally- made and existing benchmark miniplate and screw fixation.

STUDY DESCRIPTION

Research Design

This study will be performed on patients with maxillofacial fractures. The study is a blind randomized clinical study comparing locally-made titanium plate and screws with the existing benchmark, BIOMET® miniplate, and screw. After fixation, bone density, local tissue reactions, and screw loosening between these two devices at specific periods will be compared.

Time And Place

The clinical study will be conducted at Cipto Mangunkusumo Hospital, Jakarta, Indonesia from September 2019 – April 2020. Surgery will take place at Cleft Craniofacial Center Operating Theatre. It will be conducted by two consultants of craniomaxillofacial surgeons.

STUDY POPULATION

Inclusion Criteria

- Midface fracture with the indication of surgery
- Midface fracture sustained within 2 weeks

Exclusion Criteria

- Comminuted and defect fracture

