- Midface fracture on patients with systemic diseases affecting bone healing.
- Midface fracture in children
- Midface fracture in multiple trauma patients with neurological deterioration

Dropout Criteria

- Patient who is unable to complete radiological evaluation after surgery due to lost to follow up or refuse to continue the evaluation will be replaced by another sample
- Patient with signs of bacterial infection either locally or systemically or implant failure are not dropouts, their last data of observation will be included and analyzed (Last-Observation-Carried-Forward (LOCF) method).

METHODOLOGY

Subject Allocation

Subject is the fracture line found on the patient. The surgeon is not blinded on which miniplate is going to use because the miniplate has different characteristic.

Intervention

Pre-operatively

- Patients will sign the informed consent sheet and declare that they want to be enrolled as subjects and obey all the instructions given postoperatively
- The patients will shower with chlorhexidine 4% 27 soap 1 day before surgery
- An empiric antibiotic will be administered 1 hour preoperatively: intravenous injection of Ampicillin Sulbactam 1.5 gr/IV 28 to prevent postoperative infection.

Intra-operatively

- All patients will be treated under general anesthesia.
- After induction of anesthesia, the operating field is disinfected with povidone-iodine
- Draping the patient, exposing only the area of surgery
- Local anesthetic solution with a vasoconstrictor is administered along the incision line area for homeostasis
- Maxillary mandibular fixation is performed to maintain the occlusion
- Midface fracture site approach through an intra-oral or extra-oral incision according to the accessibility at that time and may differ for every patient
- The fractured segment is reduced into proper position using Carroll-Girrard, hook, elevator or Rowe disimpaction forceps.

- The surgeon will received a seal envelope contain an instruction to use locally-made miniplate or existing benchmark miniplate and then it will be bend as desired based on the fracture site contour
- The surgeon will place the miniplate on the fracture site based on AO/CMF point fixation sequence.
- The plate is tapped manually with gentle pressure. The screw is inserted into the hole using a screwdriver and held parallel to the long axis of the drill hole.

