After completing the procedure, subjects will undergo non-contrast head CT scan evaluation immediately after surgery as a baseline, and by the end of 3rd months post-operation. Afterward, a radiologist consultant as a blinded independent evaluator will assess the bone density score in each subject. A score sheet will be given to the assessor. Subjects will also be instructed to visit the outpatient clinic once a week for 3 weeks post-operatively to evaluate their appearances clinically if there is any sign of bacterial infection or local tissue reaction that will be taken care of by consultants of craniomaxillofacial surgeons.

Bone Density

Bone density of each subject will be recorded in Hounsfield Unit (HU). The bone density score of each subject will be noted and scores between the two brands will be compared. The scores will be evaluated by a radiologist consultant and act as an independent evaluator after the subject has completed all their Head CT evaluation.^{29, 30}

[figure not shown]
Screw Loosening

Screw loosening will be recorded, whether it is present or not. It will be evaluated by a radiologist consultant after the subject completed all their Head CT evaluation.

Tissue reaction

Local tissue reactions such as edema, bacterial infection, or any other signs of the inflammation process, will be recorded by the end of the 3rd week during patient's visit outpatient clinic. It will be evaluated by consultants of craniomaxillofacial surgeons and.

Research Protocol

DATA ANALYSIS AND DATA PRESENTATION

Data on bone density are quantitative, all scores from points of evaluation group will be collected, and scores for the dependent variables between groups will be statistically compared using independent t-test or Mann Whitney test depending on the distribution of the data is normal or not. Other findings will be presented using descriptive statistics.

Table 2. Dummy table of bone density (HU) in group I (Locally-made miniplate and screw) versus group II (existing benchmark miniplate and screw) at different observation periods.

Time (Postop)	Group I (Mean ±SD)	Group II (Mean ±SD)	p-Value*
Bone Density			
Immediately post op			
Three months post op			

*Statistically significant difference versus baseline reading if p-value ≤ 0.05 HU=Hounsfield unit.

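### The plan lets an assessor who knows the plate score tissue reaction, a judgement-based outcome in the hypothesis of a study labelled blind

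*Combined protocol and SAP*

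**What the plan says.** The Research Design section describes the trial in these words: "The study is a blind randomized clinical study". It does not say who is blinded. Time And Place says of the surgery: "It will be conducted by two consultants of craniomaxillofacial surgeons". Subject Allocation then states: "The surgeon is not blinded on which miniplate is going to use because the miniplate has different characteristic".

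The Study Hypothesis claims non-inferiority "in terms of bone healing, surrounding tissue reactions, and screw loosening". Tissue reaction is also listed as a secondary objective.

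Under Assessing Study Results, the Tissue reaction subsection defines the outcome as "Local tissue reactions such as edema, bacterial infection, or any other signs of the inflammation process", recorded by the end of the third week at the outpatient clinic. Of the assessor it says: "It will be evaluated by consultants of craniomaxillofacial surgeons and". The sentence stops at that point. The opening paragraph of the same section says of the weekly clinic checks for infection and tissue reaction "that will be taken care of by consultants of craniomaxillofacial surgeons".

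That paragraph also gives the bone density reading to an independent radiologist who is said to be blinded. The data analysis section plans a test for bone density only; all other findings are descriptive. Table 3 shows tissue reaction as present or absent at the third week, with 60 per group.

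**The concern.** Whether mild edema or some other inflammatory sign counts as a reaction is a clinical judgement, and the plan gives no threshold or checklist. An assessor who knows which plate lies under the wound may call borderline cases differently for the two products. The plan guards against this for a numerical CT reading but writes no such guard for the outcome that depends most on judgement.

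At stake is the tissue-reaction part of the hypothesis. No margin or test is planned for it, so readers will judge that claim from the counts in Table 3. If those counts depend on what the assessor knew, neither a difference nor a similarity between the groups can be read with confidence. The label 'blind' would lead a reader to think this had been dealt with.

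**Working it through.** The plan states no figure to reproduce. The question is who scores each outcome and what that person knows, so the check sets the statements side by side.

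| Item | Who | Knowledge of the plate, as written |
|---|---|---|
| Surgery | Two craniomaxillofacial consultants | Operating surgeon not blinded |
| Bone density | Radiologist | Described as blinded and independent |
| Screw loosening | Radiologist | Not stated in that subsection |
| Tissue reaction | Craniomaxillofacial consultants, sentence incomplete | Not stated |

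1. **Same role.** The operators and the tissue-reaction assessors come from the same specialty and grade. The document does not say they are the same individuals.

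2. **Unblinded role.** The operating surgeon receives the envelope in theatre and, according to Subject Allocation, can tell the plates apart. Any consultant who operated on a patient therefore knows the allocation when that patient attends clinic.

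3. **No separation rule.** Subject Allocation, Intervention, Miniplate And Screw Placement and Assessing Study Results contain no requirement that the clinic assessor be a non-operator, or be kept from the envelope, the operative note or the post-operative CT. The blinding statement for the radiologist is attached to bone density and is not extended to the clinic.

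4. **Judgement-based outcome.** The definition ends in an open category covering any other inflammatory sign. Table 3 reduces it to presence or absence. A yes/no format does not remove judgement, because someone must still decide where presence begins.

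5. **Scale.** The plan gives no expected reaction rate and no misclassification rate, so a bias cannot be estimated from it. The only scale available is the denominator in Table 3: one fracture line scored differently changes a group's percentage by 1/60 = 0.0167, about 1.7 points, up or down. That is the weight of one call, not an estimate of how many calls would be wrong.

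Steps 1 to 4 together show that the plan allows unblinded scoring. They do not show that it will happen in every case.

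**The case against.** The strongest reply is that the point rests on silence. The text names a role, not a person, and a consultant who did not operate could be doing the scoring unaware of the plate. The assessor sentence is incomplete, so a further assessor may have been intended or the words may have been lost in conversion. The outcome is secondary and descriptive, so there is no formal comparison to bias. The surgeon's unblinded status is disclosed openly, which makes the label 'blind' imprecise rather than misleading by intent.

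Most of this stands, and it limits the claim. It does not remove it: a safeguard that might be followed informally is not part of the plan, and even with another assessor added the craniomaxillofacial consultants would still be assessors.

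A reader might infer four stronger things that the documents do not support:

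- *That surgeons score their own patients, so the outcome is known to be unblinded.* The text shows a shared role only.
- *That bias would favour the local plate.* The background gives cost and policy reasons for wanting it to succeed, but a surgeon wary of a new device could equally over-call reactions with it. The direction is open.
- *That the primary outcome is compromised.* Bone density is read by a radiologist described as blinded. The Dropout Criteria do carry forward the last observation for patients with signs of infection, but they do not say who makes that call or tie it to the week-3 score.
- *That one of the two consultants is always free to assess blind.* The statement about two consultants could mean that both operate on a case, so the remedy must allow for that.

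**Conclusion.** The concern holds in this form: the plan permits unblinded scoring of a judgement-based secondary outcome that is named in the hypothesis, in a study called blind without saying who is blinded. The consequence is limited to the descriptive tissue-reaction counts in Table 3, but these are the only evidence planned for that part of the non-inferiority claim.

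Neither the size nor the direction of any bias can be derived from the documents. The conclusion assumes that the missing end of the assessor sentence does not contain a masking rule; the sponsor can check that at once against the source file. It is worth correcting before enrolment because the remedy is cheap, but it does not threaten the primary comparison.

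**What to change.** 1. Complete the assessor sentence in the Tissue reaction subsection.
2. State there that, at the existing week-3 visit, each fracture line is scored on a fixed yes/no checklist (edema, infection, other inflammation) by the craniomaxillofacial consultant who did not operate on that patient and has not seen the envelope, the operative note or the post-operative CT. The CT belongs on the list because the plates are said to differ and the plan does not say whether the difference shows on imaging.
3. Where both consultants operated, record the score as unblinded, and report the number of unblinded scores with Table 3.
4. In Research Design, replace the general term 'blind' with a statement of who is blinded: surgeon unblinded; radiologist blinded for bone density; tissue-reaction assessor blinded where the rule in item 2 is met.

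The cost is protocol wording, a short checklist and some clinic scheduling between the existing consultants. The drawback is that a patient may not see their own surgeon for the scored check. No extra staff or visit is needed. If both consultants usually operate together, most scores will be unblinded; the fix will then make the limitation visible rather than remove it.

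### The hypothesis is non-inferiority on three outcomes, but the planned analysis is a difference test on bone density with no margin or decision rule

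*Combined protocol and SAP*

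**What the plan says.** Aim Of The Study sets out to show that the local plate and screws "are not inferior compared to the existing benchmark miniplate and screw in terms of bone healing, surrounding tissue reactions, and screw loosening". Study Hypothesis repeats this for the same three outcomes.

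The Primary Objective is "To evaluate bone density radiologically (in Houndsfield Unit) after plate and screw fixation", local against benchmark. The secondary objectives are more modest. The one on loosening reads "To evaluate if there is any loosening screw following both locally-made and existing benchmark miniplate and screw fixation", and the one on local tissue reaction is worded in the same way.

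Data Analysis and Data Presentation has bone density scores "statistically compared using independent t-test or Mann Whitney test depending on the distribution of the data is normal or not". It then says "Other findings will be presented using descriptive statistics". Dummy Table 2 shows mean ± SD by group and a p-value column, with the footnote "Statistically significant difference versus baseline reading if p-value ≤ 0.05". Dummy Table 3 has 60 per group and no inferential column. Under Subject Allocation, "Subject is the fracture line found on the patient", so the 60 are fracture lines.

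**The concern.** The t-test and the Mann-Whitney test both take no difference as the null hypothesis. A non-significant result says only that the data did not show a difference; it does not exclude a plate that is worse by an amount that matters. Non-inferiority needs a margin fixed in advance and an interval, or a test with a shifted null, judged against it. The analysis section has neither.

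If a non-significant result is then read as not inferior, the incentive runs the wrong way: the smaller or noisier the study, the easier the claim. At stake is the trial's main conclusion, which is meant to support using a cheaper local implant in place of imported ones.

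For tissue reaction and loosening the fault is different. Descriptive reporting fits the secondary objectives; it is the hypothesis that claims more than they ask for.

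The threshold is also badly worded. The Table 2 footnote ties p ≤ 0.05 to a difference from baseline, while the text and the table columns compare the two groups.

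**Working it through.** **Inputs from the documents.** 60 lines per group (Table 3 heading); 0.05 threshold (Table 2 footnote); t-test as the main analysis; CT at baseline and 3 months.

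**Not in the supplied text.** Margin, SD of HU, power and sidedness. The 60 per group therefore cannot be reproduced, and results are given in SD units.

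**Assumptions.** Two-sided 5% test, higher density is better, and (steps 1 to 4) independent lines.

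**1. Risk of a false claim if p > 0.05 is read as not inferior.** Let the true deficit d equal the margin. The t statistic is noncentral t with 118 degrees of freedom and noncentrality d × √(60/2); the critical value is 1.980.

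| True deficit = margin | Noncentrality | P(p > 0.05) |
|---|---|---|
| 0.3 SD | 1.643 | 0.629 |
| 0.4 SD | 2.191 | 0.416 |
| 0.5 SD | 2.739 | 0.225 |

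A rule requiring the lower limit of a two-sided 95% interval to lie above minus the margin gives 0.025 in every row.

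**2. What a non-significant result leaves open.** The half-width of the 95% interval is 1.980 × √(2/60) = 1.980 × 0.1826 = 0.362 SD. A deficit that just misses significance has an interval reaching about −2 × 0.362 = −0.72 SD.

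**3. Margin that 60 per group can support** (one-sided 2.5%, true difference zero):
- 80% power: (1.960 + 0.842) × 0.1826 = 0.51 SD
- 90% power: (1.960 + 1.282) × 0.1826 = 0.59 SD
- Adjusting for baseline, with an assumed baseline to month-3 correlation of 0.5: 2.802 × √((2/60) × 0.75) = 0.44 SD at 80% power

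**4. Lines per group for a tighter margin M**, 80% power, n = 2 × 2.802² / M²:
- M = 0.4 SD: 98.1, so 99
- M = 0.3 SD: 174.4, so 175

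At 60 per group, power is 58% for 0.4 SD and 37% for 0.3 SD (noncentral t).

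**5. Sensitivity to lines within patients.** Assume two lines per patient with correlation 0.5, and apply the planned unadjusted test. The variance of the difference is (2/60) × 1.5 if both lines get the same plate and (2/60) × 0.5 if each line gets a different plate (normal approximation, critical value 1.980).

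| | Same plate | One line per plate |
|---|---|---|
| P(p > 0.05), deficit 0.3 SD | 0.61 | 0.68 |
| P(p > 0.05), deficit 0.5 SD | 0.27 | 0.14 |
| Margin at 80% power, correct model | 2.802 × √0.0500 = 0.63 SD | 2.802 × √0.0167 = 0.36 SD |

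**6. Binary outcomes** (Newcombe 95% interval for the risk difference, independent lines):
- 0/60 v 0/60: each Wilson upper limit is 0.060, giving ±6.0 percentage points
- 3/60 v 3/60: each Wilson interval is 0.017 to 0.137, giving ±√(0.087² + 0.033²) = ±9.3 percentage points

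Even identical low counts therefore leave an excess of several percentage points open.

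**The case against.** The strongest reply is that the error rates describe a misreading the plan never states. It nowhere says that p > 0.05 will be called not inferior, and the mean ± SD in Table 2 would let a reader derive a difference and an interval. That is right, and the 63%, 42% and 22% are conditional on that reading. It does not rescue the plan, because a derived interval has no pre-specified margin to be judged against and the analysis section offers no other inferential route to the hypothesis.

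Second, part of the document was removed before review and no sample size section is supplied, so a margin may be stated there. It may. The analysis section is supplied, however, and neither uses nor refers to one.

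Third, a supportable margin of 0.51 SD assumes independent lines. This stands: the range of 0.36 to 0.63 SD from step 5 belongs beside it.

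Fourth, a margin with an interval rule is enough to cure this fault. Baseline adjustment and dropping the normality-driven choice of test are improvements to the estimate. That is fair. The Dropout Criteria (last observation carried forward for infection or implant failure, replacement of patients lost to follow-up) could also affect a non-inferiority comparison; that is a separate matter which the margin does not settle.

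Finally, the footnote can be called a slip, since the table plainly compares groups. It is minor, but it is the only place in the supplied text where a threshold is given.

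**Conclusion.** The concern holds, and the plan should be changed before the results are analysed. As written, the analysis cannot support a conclusion of non-inferiority on any of the three outcomes. This rests on the text of the hypothesis and the analysis section, not on any numerical assumption.

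The size is illustrative. In the clustering cases computed, the chance of a false claim runs from 61% to 68% at a margin of 0.3 SD and from 14% to 27% at 0.5 SD, all far above 2.5%. These figures assume 60 lines per group, a two-sided 5% test and non-significance read as not inferior. They cannot be converted to HU because the supplied text gives no SD.

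**What to change.** Before any month-3 scan is read:

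- Pre-specify a margin in HU and justify it on clinical grounds, not by what the sample can support.
- Estimate the local minus benchmark difference in month-3 HU with a two-sided 95% confidence interval, from a linear model with baseline HU and a patient random effect. This replaces the choice between t-test and Mann-Whitney.
- Conclude non-inferiority on bone density only if the lower limit lies above minus the margin.
- For tissue reaction and screw loosening, report risk differences with 95% intervals that allow for lines within the same patient, and remove both outcomes from the non-inferiority hypothesis.
- Correct the Table 2 footnote so that it describes the between-group comparison.
- If no margin can be justified, or the sample cannot support it, restate the aim as estimating the difference and drop the not-inferior conclusion.

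**Cost.** The baseline CT is already collected. The change is one of wording and analysis only if the justified margin is about 0.51 SD or wider for 80% power (0.59 SD for 90%) with independent lines. With two correlated lines per patient, as assumed in step 5, the 80% threshold could lie anywhere from 0.36 to 0.63 SD, depending on how plates are shared out within patients. A tighter margin needs more lines (99 per group at 0.4 SD, 175 at 0.3 SD, if independent) or giving up the claim. Restating the aim as estimation needs no extra patients. The conclusion may be less favourable to the local plate.

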- The steps of drilling, tapping and screwing all panel holes are repeated for all screw holes followed by the closure of the incision with usual manner.
- The maxillary mandibular fixation is removed and the jaw is manipulated to evaluate the occlusion and also measure the maximal mouth opening. Forced-duction test is performed when there is a placement of the plate on the orbital rim.
- The maxillary mandibular fixation is maintained for approximately 2 weeks and evaluates once a week during patient visit to the outpatient clinic

Post-operatively

- Intravenous injection of Ampicillin Sulbactam 1.5 gr every 6 hours is given for 1-2 days, then when the patient is discharged it is replaced by Amoxicillin/clavulanic acid 625 mg orally every 8 hours for another 7 days post-operatively
- Intravenous injection of Paracetamol 1 gr every 8 hours is given for 2 days followed by oral tablets 500 mg every 8 hours as needed for another 7 days for pain control
- All patients undergo a non-contrast head CT scan on day one postop as a baseline
- All patients are discharged two days after surgery and instructed to have liquid diet for 2 weeks post-operatively
- Patients will visit the outpatient clinic once a week for 3 weeks. Sign of bacterial infection or local tissue reaction will evaluate by the end of 3rd week
- All patients performed a non-contrast head CT scan at 3 months postoperatively.

Miniplate And Screw Placement

Once a patient lies down on the operating table under general anesthesia, the surgeon will identify the fracture segment. The surgeon will received a seal envelope contain an instruction to use locally-made miniplate or existing benchmark miniplate to be placed on the fracture site according to a predetermined randomization list. The decision where to place the locally made miniplate or existing benchmark miniplate depends on AO/CMF point of fixation sequence.

Assessing Study Results

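### The primary HU comparison pools midface sites and uses neither site nor same-line day-1 HU: a possible loss of precision of unknown size, not a bias

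*Combined protocol and SAP*

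**What the plan says.** Under Subject Allocation the unit of study is the line: "Subject is the fracture line found on the patient". The first inclusion criterion is "Midface fracture with the indication of surgery", with no restriction to one anatomical site. The intra-operative steps show that more than one site is expected: "Forced-duction test is performed when there is a placement of the plate on the orbital rim". The same list lets the incision be intra-oral or extra-oral, "according to the accessibility at that time and may differ for every patient". That sentence concerns the surgical approach and bears on the plated site only indirectly.

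Under Miniplate And Screw Placement, "the surgeon will identify the fracture segment" and then receives the sealed envelope. The list is described as predetermined, and no stratification by site is stated.

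The primary objective is bone density in HU. CT is taken on day one as a baseline and again at 3 months. Under Data Analysis And Data Presentation, scores are to be "statistically compared using independent t-test or Mann Whitney test depending on the distribution of the data is normal or not". Table 2 has one row per time point and one column per group, and its footnote gives p ≤ 0.05. Day-1 HU appears there as a separate row, not as a covariate. The study hypothesis is that the local plate is not inferior.

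**The concern.** A two-group test on raw HU treats every difference between lines, other than the plate, as noise. If an orbital rim line and a line elsewhere in the midface have different native density, that difference enters the error term. Two pieces of information that could remove it are available for every line: the site, identified before the plate is assigned, and day-1 HU, measured on the baseline CT. The planned tests use neither.

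What is at stake is the width of the interval for the HU difference. A non-inferiority claim rests on that interval. The visible text gives no margin and no interval, only the p-value criterion under Table 2. If non-significance were taken as support for the hypothesis, added noise would favour the hoped-for conclusion.

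**Working it through.** **Inputs.**
- Lines per group: 60, from the column headings of dummy Table 3 (tissue reaction and screw loosening). Table 2 gives no n.
- Level: 0.05, from the Table 2 footnote. Sidedness is not stated; two-sided is assumed.
- Share f of HU variance lying between sites: not in the documents, so a range is assumed.
- Lines treated as independent: assumed.

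The visible text gives no HU standard deviation, effect size, margin or power, so there is no figure of the plan's own to reproduce.

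**Step 1: site alone.** Adjusting for site multiplies the error variance by (1 − f). The standard error falls by 1 − √(1 − f), and the adjusted analysis is worth 60/(1 − f) lines per group. In units of the within-site SD, the unadjusted 95% half-width is 1.96 × √(2/60) / √(1 − f). Power of the unadjusted test at a true difference of 0.5 within-site SD is Φ(0.5 × √(60(1 − f)/2) − 1.96).

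| f | Cut in SE by adjusting | Worth, lines per group | Unadjusted half-width | Unadjusted power |
|---|---|---|---|---|
| 0 | 0% | 60 | 0.358 | 0.78 |
| 0.1 | 5% | 66.7 | 0.377 | 0.74 |
| 0.2 | 11% | 75 | 0.400 | 0.69 |
| 0.3 | 16% | 85.7 | 0.428 | 0.63 |
| 0.4 | 23% | 100 | 0.462 | 0.56 |
| 0.5 | 29% | 120 | 0.506 | 0.49 |

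With site in the model the half-width is about 0.358 at every f, apart from a few degrees of freedom.

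**Step 2: day-1 HU already in the model.** If site still explains 5% to 15% of the remaining variance, its added worth is 60/0.95 = 63.2 to 60/0.85 = 70.6 lines per group, relative to 60 analysed with day-1 HU alone.

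An illustration, with all values assumed: the site share is 0.3 at both scans and the within-site correlation between scans is 0.5. The overall correlation is 0.3 + 0.7 × 0.5 = 0.65. Residual variance, as a share of the total, is:
- site alone: 0.70
- day-1 HU alone: 1 − 0.65² = 0.58
- both: 0.7 × (1 − 0.5²) = 0.53

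Here day-1 HU does more than site, and adding site removes about a further 9%. With a weak within-site correlation, site alone could do better.

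**Step 3: validity.** A simulation used four equally common sites and 60 versus 60 lines, with f = 0, 0.2, 0.4 and 0.6. It had 6,000 runs per setting for the t-test and the site-adjusted model, and 3,000 for Mann-Whitney.
- With no true difference, the t-test rejected in 0.047 to 0.052 of runs and the site-adjusted model in 0.050 to 0.055. Mann-Whitney gave 0.042 to 0.061, with no trend in f.
- The unadjusted mean difference was unbiased at every f.
- At a true difference of 0.5 within-site SD, t-test power was 0.78, 0.69, 0.56 and 0.41; Mann-Whitney gave 0.76, 0.66, 0.53 and 0.37. The site-adjusted model stayed at 0.76 to 0.77.

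**Step 4: the p-value criterion.** If the local plate were truly worse by 0.5 within-site SD, the chance of a non-significant t-test would be 1 − 0.78 = 0.22 at f = 0, rising to 0.31, 0.44 and 0.59 at f = 0.2, 0.4 and 0.6.

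**The case against.** The strongest reply is that nothing here is invalid. With sound randomisation the pooled test is unbiased and holds its level, so omitting a covariate is a choice about efficiency. That stands. A reader might infer that mixing sites biases the plate comparison or inflates false positives; step 3 shows otherwise. Nor is chance imbalance in site between arms a second harm, because the unadjusted standard error already allows for it.

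The premise is also unproven. A reader might take it as established that midface sites differ in HU. The documents give no HU by site, no HU standard deviation and no mix of sites. If f is zero there is nothing to gain, and adjusting costs slightly: simulated power was 0.763 adjusted against 0.776 unadjusted.

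The upper figure of 120 lines is likewise not an estimate. It assumes independent lines, half of all HU variance between sites, and no use of day-1 HU. The trial already collects day-1 HU, which may carry much of the site difference, so the further gain from site is probably smaller. This stands too, and is why the remedy should include both.

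Finally, the visible plan has no margin, so the gain in precision is not yet tied to a stated decision rule. That limits how the benefit can be expressed, but step 4 shows that noise is not harmless under the only criterion given.

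**Conclusion.** The point holds as a loss of precision of unknown size. The primary HU test pools lines from different midface sites and ignores two measurements that could reduce the error variance. Adjusting for site alone is worth between 60 lines per group (no gain) and 120, for an assumed site share of 0% to 50%. Once day-1 HU is in the model, an assumed partial share of 5% to 15% makes site worth about 63 to 71. Both ranges assume independent lines and take the 60 per group from a dummy table.

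The documents do not support a claim of bias or of inflated type I error. Two neighbouring questions are separate and not needed here: several lines from one patient, and whether the fixation sequence ties plate to site. The change is worth making because it is cheap and because the non-inferiority hypothesis gains directly from a narrower interval.

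**What to change.** Record one anatomical site code per line before the envelope is opened, so that the code cannot depend on the assigned plate. Replace the t-test or Mann-Whitney choice for the primary comparison with a prespecified linear model for 3-month HU containing plate, the same line's day-1 HU and a few site groups defined before any HU is read (for example orbital rim, buttress, other). Report the adjusted HU difference with its confidence interval. Separate envelope stacks by site group would balance the plates within site, but are optional.

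The cost is a few degrees of freedom and one code per line that the surgeon already knows. No extra patients, scans or visits are needed. If lines from one patient are analysed together, the model must also allow for that, whichever covariates are used.
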